#### 5.3.2 Multiple Measurements within Visit Windows

If more than one assessment falls within a given window then the assessment closest to the target study day will be selected for the by-visit summaries. If two assessments are equidistant from the target day then the chronologically last assessment will be used for summary. Exceptions may be made for incomplete assessments, in which case, more complete assessments may be given priority. If multiple measurements occur on the same day

at the same time (or the time is not available), the average of the measurements will be taken. Details are provided in a separate programming specifications document.

For safety summaries where the most extreme post-baseline values should be selected, e.g. overall post-baseline minimum and overall post-baseline maximum, all non-missing post-Baseline values should be considered, regardless of whether the value is selected for the by-visit summaries.

When replicate ECGs are collect at a given timepoint (typically, in triplicate), the average of the replicate values (i.e., PR interval, QRS duration, QT interval, QTcB interval, QTcF interval, and RR interval) will be considered as one assessment for the analyses.

### **5.3.3 Data Listings**

All results will be presented in data listings, and the values selected for analysis will be marked.

## **5.4 Data Handling Conventions**

### **5.4.1 Missing or Incomplete Date for Last Dose of Study Drug**

In the Safety Analysis Set, if the last dose date of study drug is missing for a subject who completed or early terminated from the study, then the missing last dose date of study drug will be imputed using the last expected dosing date which is defined as the minimum of the non-missing drug return date of the last dispensed drug kits, the last drug dispensed date plus the number of days that the dosing would continue per protocol or the end-of-treatment/early termination visit (EOT/ET) date, whichever occurs earlier. For the incomplete last dose date of the study drug, the imputation will be compared against the last expected dosing date defined as above. Detailed algorithms will be documented in a separate programming specifications document. The missing or incomplete dates will be displayed in the data listings as reported on the eCRF rather than the imputed dates.

For data summarizations before final database lock, if a subject is still ongoing, then the subject's last dose date will be imputed using the database cutoff date.

### **5.4.2 Missing or Incomplete Dates for Concomitant or Post-Treatment Medications**

Missing or incomplete medication start or end dates will be imputed for the purpose of determining whether the medications are taken concomitantly (see [Section 10](#) for definition). When the chronological order of medication use relative to the study drug treatment period is unclear due to missing or incomplete date(s), the medication will be considered as concomitant. The imputation algorithms will be detailed in the programming specifications

document. The missing or incomplete dates will be displayed in the data listings as reported on the eCRF rather than the imputed dates.

#### **5.4.3 Missing or Incomplete Dates for Adverse Events**

Missing or incomplete adverse event (AE) start dates will be imputed for the purpose of determining whether the AEs are treatment-emergent (see [Section 13.1](#) for definition). When the chronological order of an AE onset relative to the study drug treatment period is unclear due to missing or incomplete date(s), the AE will be considered as treatment-emergent. The imputation algorithms will be detailed in the analysis dataset specification document. The missing or incomplete dates will be displayed in the data listings as reported on the eCRF rather than the imputed dates.

#### **5.4.4 Missing Severity Assessment for Adverse Events**

If the severity is missing for a treatment-emergent AE, a severity of “Severe” will be assigned. The imputed values for severity assessment will be used for incidence summaries, and the actual values will be presented in data listings.

#### **5.4.5 Missing Relationship to Study Drug for Adverse Events**

If the relationship to study drug is missing for a treatment-emergent AE, a causality of “Related” will be assigned. The imputed values for relationship to study drug will be used for incidence summaries, and the actual values will be presented in data listings.

#### **5.4.6 Character Values of Clinical Laboratory Variables**

If the reported value of a clinical laboratory variable cannot be used in a summary due to, for example, a character string reported for a numeric variable, an appropriately determined coded value will be used in the summary. The coding algorithms will be detailed in the analysis dataset specification document. The actual values as reported in the database will be presented in data listings.

### **6 SUBJECT DISPOSITION**

The number of sites that screened at least 1 subject, number of sites that enrolled at least 1 subject, number of subjects screened, and number of unique subjects screened will be summarized. In addition, the number of subjects enrolled at each site will also be tabulated.

For enrolled subjects, the number and percentage of subjects in the analysis sets will be summarized. A listing will be provided displaying all subjects excluded from the analysis sets (if any), and will include reason(s) for exclusion.

For subjects who participate in the screening phase and are screen failures, their demographics information (including age, sex, ethnicity, and primary race), screen failure reasons (the specific inclusion/exclusion criterion [or criteria] not met or other reason), informed consent information, and protocol version will be provided in a listing. If a subject is re-screened, then the re-screening subject ID and the final enrollment status (whether eventually enrolled) will also be displayed in this listing. In addition, the frequency that the screen failure reasons are reported will also be summarized. Note that a subject may be deemed ineligible for multiple inclusion/exclusion criteria and may be allowed to rescreen with the permission of the Medical Monitor, provided the screen failure was due to a temporary condition that subsequently resolved.

Early terminations of subjects due to COVID-19 related reasons will be captured in the eCRFs and tabulated. The number and percentage of subjects who completed the study or discontinued (all discontinued and by discontinuation reason) will also be summarized for the Safety and Full Analysis sets.

## 7 PROTOCOL DEVIATIONS

Protocol deviations will be reviewed periodically over the course of the study. The review process, definition of the deviation categories, and the classification of a deviation as major or minor will be detailed in the study Protocol Deviation Management Plan. Protocol deviations will also be assessed with respect to relationship to COVID-19.

For Safety subjects, a summary of the number and percentage of subjects with major protocol deviations for each deviation category will be presented by relationship to COVID-19 (overall, COVID-19 related, and non-COVID-19 related). A listing of all protocol deviations will also be provided by relationship to COVID-19 (overall, COVID-19 related, and non-COVID-19 related).

## 8 DEMOGRAPHICS AND OTHER BASELINE CHARACTERISTICS

Demographics and baseline characteristics will be summarized for the Safety and Full Analysis sets using descriptive statistics.

Variables include age, sex, primary race (subjects of multi-racial background can only identify/select one primary race on eCRF, or choose “other” and specify), ethnicity, height, weight, body mass index (BMI), childbearing potential, subject/caregiver living situation, and caregiver relationship.

The reported age reflects a subject’s age at the informed consent date. Age and BMI will be presented as both continuous and categorical variables. Age categories will be presented as

<65, 65 to 74, 75 to 84, and ≥85 years old. BMI categories (kg/m^2) will be presented as <25, 25 to 30, and >30. Race will be categorized as White vs. Non-White.

## **8.1 Baseline Disease Characteristics**

Disease characteristics at Baseline will be summarized for the Safety and Full Analysis sets using descriptive statistics. MMSE total score, CGI-S, NPI-Q nighttime behavior (severity and distress), MDS-UPDRS Part I total score, and MDS-UPDRS Part II total score, will be presented as continuous variables. CGI-S and NPI-Q will also be presented as categorical variables using discrete categories. The number and percentage of subjects reporting suicidal ideation (within the past 6 months) and suicidal behavior (within the past 12 months) and lifetime, and suicidal ideation or behavior since the Screening visit, will be tabulated.

## **8.2 Neuropsychiatric Inventory**

Baseline NPI will summarized for the Safety and Full Analysis sets using descriptive statistics. The delusions total score, hallucinations total score, and psychosis total score will be presented as continuous variables. In addition, for each of the delusions and hallucinations domains the frequency, severity, and distress scores will be presented as categorical variables.

## **9 MEDICAL HISTORY**

Medical and surgical history data will be coded using Medical Dictionary for Regulatory Activities (MedDRA) version 23.0 or newer. The subject incidence will be summarized for each system organ class (SOC) and preferred term for the Safety Analysis Set and Full Analysis Set. A subject will be counted only once per SOC or per preferred term for the summary.

A listing of the SOC, preferred term, body system, verbatim term for the medical history condition/event, start and stop dates (when available), and an indicator for whether or not the condition is ongoing at Screening will be provided.

## **10 PRIOR, CONCOMITANT, AND POST-TREATMENT MEDICATION**

Medications will be coded using WHO Drug Dictionary (WHODRUG-Global-B3) March 2019 or later. Relationship to COVID-19 will be assessed by the investigator as specified in the DMP, Appendix B.

For medications, the number and percentage of subjects taking each drug class (ATC Level 3) and medication preferred term will be tabulated. A subject will be counted only once per drug class or per medication preferred term for the summary. Prior, concomitant, and

post-treatment medications will be summarized separately using the Safety Analysis Set. Concomitant medications will also be summarized by relationship to COVID-19.

Listings of the prior, concomitant, and post-treatment medications will also be provided.

Prior medication is defined as any medication with a start and stop date prior to the date of the first dose of study drug.

Concomitant medication is defined as any medication with a start date prior to the date of the first dose of study drug and continuing after the first dose of study drug, or with a start date between the dates of the first and last doses of study drug, inclusive.

Post-treatment medication is defined as any medication with a start date after the last dose of study drug.

## **11 EXTENT OF EXPOSURE AND TREATMENT COMPLIANCE**

Summaries of exposure and compliance to study drug will be provided for the Safety Analysis Set using descriptive statistics.

### **11.1 Exposure to Treatment**

Pimavanserin dose levels are expressed as free base.

Duration of pimavanserin exposure (days) for each subject is calculated as follows:

$$\text{Duration of exposure} = \text{last dose date} - \text{first dose date} + 1$$

The number and percentage of subjects in each of the following categories will be displayed:  $\leq 2$  weeks (1 to 14 days),  $\leq 4$  weeks (1 to 28 days),  $\leq 8$  weeks (1 to 56 days),  $\leq 12$  weeks (1 to 84 days), and  $\leq 16$  weeks (1 to 112 days). An additional category may be added depending on the length of maximum exposure.

### **11.2 Measurement of Treatment Compliance**

Treatment compliance is defined as the total number of tablets actually taken by a subject divided by the number of tablets expected to be taken while on treatment, then multiplied by 100. The total number of tablets actually taken is calculated by the total number of tablets dispensed minus the number of tablets returned. The number of tablets expected to be taken is calculated as the duration of exposure multiplied by 2 (the planned number of tablets taken per day). If one or more kits are not returned, the tablets expected to be taken will be imputed; the details will be provided in the analysis dataset specification document.

Treatment compliance will be summarized descriptively as both continuous and categorical variables. For the categorical presentation, the number and percentage of subjects in each of the following categories will be presented: <80%, 80 to 120%, and >120%.

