Exploratory Objectives To assess the extent to which caregivers and families experience additional demands, responsibilities, and difficulties To explore the effects of pimavanserin in subjects with PDP on: 
• Functional capacity• Cognition• Depressive symptoms• Nighttime behavior• Caregiver burden	Exploratory Endpoints 
• Change from Baseline to Week 16 on the Virtual Reality Functional Capacity Assessment Tool (VRFCAT) including total time to complete, total number of errors, and total number of forced progressions• Change from Baseline to Week 16 on the Caregiver Strain Index total score• Change from Baseline to Week 16 on the Neuropsychiatric Inventory-Questionnaire (NPI-Q) Nighttime Behavior Domain Severity and Caregiver Distress• Change from Baseline to Week 16 on the Geriatric Depression Scale (GDS) (Short Form)• Change from Baseline to Week 16 on mFSQ score by subscale
Safety Objective To assess the safety and tolerability of pimavanserin in adults with PDP	Safety Endpoints The safety and tolerability of pimavanserin will be assessed using the following: 
• Treatment-emergent adverse events (TEAEs)• Columbia-Suicide Severity Rating Scales (C-SSRS) score• Potentially clinically important (PCI) findings on:
• Physical examinations• Clinical laboratory tests• Vital signs• Electrocardiogram parameters
Number of Study Sites	Approximately 25 sites in the US will participate in this study.

Number of Subjects Planned	Approximately 89 subjects with PDP will be screened and 53 subjects are expected to be enrolled, assuming a screen failure rate of 40%. Approximately 42 subjects are expected to complete the study, assuming a 20% drop-out rate.
Test Product, Dose, and Administration	Pimavanserin 34 mg (provided as 1×34 mg capsule), administered orally, once daily

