5 INVESTIGATIONAL PRODUCT

5.1 Investigational Product Description

The investigational product will be pimavanserin 34 mg (provided as 1×34 mg capsule). Capsules will be administered orally as a single dose once daily.

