5.1.1 Formulation, Appearance, Packaging, and Labeling

The Sponsor will supply pimavanserin 34 mg capsules.

Commercial pimavanserin 34 mg capsules are opaque white and light green capsules with “PIMA” and “34” printed in black. Each pimavanserin capsule contains 40 mg of pimavanserin tartrate, which is equivalent to 34 mg of pimavanserin free base. [REDACTED]

[REDACTED]

[REDACTED]

Pimavanserin is manufactured under current Good Manufacturing Practices.

During the treatment period, study drug will be distributed in a quantity sufficient to ensure the subject has an adequate supply of study drug between study visits.

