5.1.3 Dosing and Administration

Study drug will be dispensed to the subject to take home. Each daily dose consists of one capsule to be taken orally, once daily. The capsules may be taken with or without food. The first dose should be taken on the morning of the day after the Baseline visit.

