## 1 INTRODUCTION

This statistical analysis plan (SAP) provides a technical and detailed elaboration of the statistical analyses of efficacy and safety data as described in the protocol Amendment 1.0 dated 20 May 2021 and the electronic case report form (eCRF). This SAP will be approved prior to database lock. Specifications for tables, figures, and listings are contained in separate documents (ACP-103-063 Table Shells, ACP-103-063 Figure Shells, and ACP-103-063 Listing Shells, respectively).

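### SAP 11.2 counts expected intake at two tablets a day against a protocol regimen of one capsule a day, so a fully adherent subject with all kits returned scores 50% and is tabulated as <80%

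*SAP*

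**What the plan says.** SAP 11.2 takes compliance as 100 times units taken over units expected. Units taken are those dispensed less those returned. The expected number is "calculated as the duration of exposure multiplied by 2 (the planned number of tablets taken per day"). Results are summarised as a continuous variable and in three categories: <80%, 80 to 120% and >120%. The section opening sets the scope: "Summaries of exposure and compliance to study drug will be provided for the Safety Analysis Set using descriptive statistics". There is one exception to the formula: "If one or more kits are not returned, the tablets expected to be taken will be imputed", with the method left to the analysis dataset specification.

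The protocol describes a different regimen, consistently:

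- Synopsis, test product row: "Pimavanserin 34 mg (provided as 1×34 mg capsule), administered orally, once daily".
- Section 5.1: "Capsules will be administered orally as a single dose once daily".
- Section 5.1.1: "Each pimavanserin capsule contains 40 mg of pimavanserin tartrate, which is equivalent to 34 mg of pimavanserin free base", so a single capsule carries the whole daily amount.
- Section 5.1.3: "Each daily dose consists of one capsule to be taken orally, once daily".

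The SAP introduction says it elaborates the analyses "as described in the protocol Amendment 1.0 dated 20 May 2021", and SAP 18 declares no departures from the protocol's analyses.

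**The concern.** The number of units expected per day is two in the SAP and one in the protocol. The SAP also counts tablets where the protocol dispenses capsules. The dosage-form wording has no numerical effect by itself, but the multiplier does, because the numerator is a physical count of what was dispensed and not brought back. A numerator counted in capsules taken once daily over a denominator of two per day gives half the intended ratio.

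At stake is whether the compliance table can be read at all for subjects with complete kit returns. Full adherence would be shown below 80%, the same cut-off that Protocol 5.1.6 uses for significant under-compliance between visits. Over-use would be hidden, because a count of twice the schedule would look like perfect compliance. A reader of the study report could conclude that an adherent open-label cohort had largely failed to take the drug.

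**Working it through.** **Inputs**

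- Multiplier in the SAP denominator: 2 per day (SAP 11.2).
- Planned units per day in the protocol: 1 capsule (Synopsis, 5.1, 5.1.3).
- Units taken: dispensed minus returned (SAP 11.2).
- Exposure days D: last dose date minus first dose date, plus 1; 16 weeks is 112 days (SAP 11.1).
- Categories: <80%, 80 to 120%, >120% (SAP 11.2).

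**The SAP's own expected count.** Over 112 days: 112 × 2 = 224 units. The protocol's regimen gives 112 × 1 = 112. The figure of 224 cannot be obtained from any legible dosing statement in the protocol.

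**Effect on the ratio, all kits returned.** Let T be units taken.

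- As written: C = 100 × T / (2 × D).
- Against the protocol schedule: C* = 100 × T / (1 × D).
- Hence C = 0.5 × C*, whatever D is.

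Full once-daily intake: 14/28 = 28/56 = 56/112 = 84/168 = 112/224 = 50.0%.

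| Intake relative to protocol schedule | Reads as | Row as written | Row against protocol schedule |
|---|---|---|---|
| 80% | 40% | <80% | 80 to 120% |
| 90% | 45% | <80% | 80 to 120% |
| 100% | 50% | <80% | 80 to 120% |
| 120% | 60% | <80% | 80 to 120% |
| 160% | 80% | 80 to 120% | >120% |
| 200% | 100% | 80 to 120% | >120% |
| 240% | 120% | 80 to 120% | >120% |

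So the 80 to 120% row as written covers 160 to 240% of schedule, and >120% needs more than 2.4 units per day.

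**What it takes to leave the <80% row.** The condition is T / (2 × D) ≥ 0.80, that is T ≥ 1.6 × D. In whole capsules:

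| Exposure (days) | 1.6 × D | Smallest count | Reads as | Above one per day |
|---|---|---|---|---|
| 14 | 22.4 | 23 | 23/28 = 82.1% | 9 |
| 28 | 44.8 | 45 | 45/56 = 80.4% | 17 |
| 56 | 89.6 | 90 | 90/112 = 80.4% | 34 |
| 84 | 134.4 | 135 | 135/168 = 80.4% | 51 |
| 112 | 179.2 | 180 | 180/224 = 80.4% | 68 |

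One capsule fewer fails: 22/28 = 78.6% and 179/224 = 79.9%.

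**With the protocol's unit count in the denominator.** Full adherence over 112 days gives 112/112 = 100% (80 to 120%), and a doubled count gives 224/112 = 200% (>120%).

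**The case against.** Several innocent readings are worth testing.

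- **Redacted text.** Part of Protocol 5.1.1 is blacked out and could mention another presentation. The legible statements in the Synopsis, 5.1 and 5.1.3 nevertheless agree on one capsule daily, so the redaction does not rescue the multiplier.
- **A regimen from the original protocol.** Where subjects enrolled under the original protocol differ, the SAP says so: the Baseline toxicity screen in 13.2.4 and the triplicate Screening ECGs in 13.2.7. Section 11.2 makes no such distinction.
- **A conversion fault.** The same sentence explains the 2 in words, so it is not a stray character.

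Other objections have some force and limit the claim. The formula does not govern subjects with unreturned kits, and their share is unknown. Capsules lost or kept count as taken, so a subject with a very short exposure could leave the <80% row on a small surplus: 1.6 × 3 = 4.8, so 5 capsules at 3 days (2 above schedule), and 1.6 × 5 = 8 at 5 days (3 above). The programming specification is a separate document and may already use one unit per day.

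On weight, the trial is exploratory with a single arm, this is one descriptive summary, and values clustering at 50% would be conspicuous. They might prompt a query, although SAP 17 refers only to standard procedures and promises no such check. None of this makes the written rule correct.

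**Conclusion.** The concern holds. SAP 11.2 contradicts the protocol on units per day and, as written, halves compliance for every subject whose kits are all returned. Full adherence reads 50% at any exposure length and is placed in <80%. At exposures of 14 days or more, leaving that row takes a surplus of 9 to 68 capsules over the durations tabulated above, so nearly all such subjects would be tabulated as <80% whatever their adherence. How many would leave it through unreturned surplus cannot be estimated, because the protocol gives no pack size or dispensed quantity.

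The result rests on two assumptions: study drug is dispensed as the protocol describes, and the SAP formula is programmed as written.

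The consequence stops at the compliance summary, both continuous and categorical. Efficacy analyses, analysis sets, exposure duration (SAP 11.1), the between-visit check in Protocol 5.1.6 and overdose reporting (Protocol 5.1.7 and 7.4.4) do not use this variable. It should be fixed, because the planned table would mislead if produced as specified.

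**What to change.** Reconcile SAP 11.2 with Protocol 5.1 and 5.1.3. Expected intake should be exposure days times the planned units per day of the protocol regimen, counted and named in the dosage form actually dispensed. Check the analysis dataset specification, including its rule for unreturned kits, and correct it if it carries the same multiplier.

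The cost is a one-line SAP correction and, if needed, a matching specification update. Data collection and all efficacy and other safety outputs stay as they are.

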5.1.6 Study Drug Compliance

If a subject misses one dose of study drug, he or she should not take an extra dose the next day.

If a subject shows significant undercompliance (<80% compliance) between any two scheduled visits, the Medical Monitor should be notified to determine if the subject remains eligible for the study and whether the incident should be considered a protocol deviation.

In the event that a subject is permanently unable to return study drug to the site (i.e., drug is lost, destroyed, or discarded), the subject/caregiver testimony is to be used in determining compliance.

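### SAP 11.2 imputes the expected count when kits are not returned, although it is the count taken that becomes unknown, and it omits the protocol's testimony rule

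*SAP*

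**What the plan says.** SAP 11.2 builds compliance from two counts.

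- **Numerator.** "The total number of tablets actually taken is calculated by the total number of tablets dispensed minus the number of tablets returned".
- **Denominator.** It is "the duration of exposure multiplied by 2 (the planned number of tablets taken per day"). SAP 11.1 takes duration from the first and last dose dates. SAP 5.4.1 supplies a fallback when the last dose date is missing.

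For missing kits, SAP 11.2 has one sentence: "If one or more kits are not returned, the tablets expected to be taken will be imputed". It adds that "the details will be provided in the analysis dataset specification document". It says nothing about how the number taken is obtained in that case.

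Protocol 5.1.6 does address the case. Where a subject is "permanently unable to return study drug to the site (i.e., drug is lost, destroyed, or discarded"), it states that "the subject/caregiver testimony is to be used in determining compliance". SAP 11.2 does not mention testimony.

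On units per day the documents also differ. Protocol 5.1.3 says: "Each daily dose consists of one capsule to be taken orally, once daily". SAP 11.2 uses two tablets. That is a separate point, but it scales every figure below.

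**The concern.** The rule repairs the term that is not broken. If a bottle does not come back, nobody knows how many capsules were left in it, so the returned count and hence the taken count are unknown. How many capsules the subject should have taken is still given by the dosing period and the daily regimen. Read as written, the returned count for that kit is zero and its whole content is treated as swallowed.

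At stake is how far the compliance table can be believed. The SAP tabulates subjects below 80%, from 80 to 120%, and above 120%. Protocol 5.1.6 uses the same 80% cut for notifying the Medical Monitor. That notification works visit by visit at the sites and is not driven by the SAP formula, but the final table is where a reader of the report would look for under-use. No pharmacokinetic samples are taken (SAP 14), so capsule counts carry real weight in describing intake.

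**Working it through.** **Inputs**

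- Taken = dispensed − returned (SAP 11.2).
- Expected = duration × 2 (SAP 11.2), or duration × 1 at one capsule daily (Protocol 5.1.3).
- Full exposure is 112 days (SAP 11.1).
- Kit size is not stated. Protocol 5.1.1 requires only that supply lasts between visits. Assumption: 28 capsules for Weeks 12 to 16, plus 0 to 7 spares. Visit windows are ±3 days (Protocol Table S-1), so an interval can run up to 6 days over, which makes some spares plausible.

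**Step 1: the SAP formula with all kits returned.** Expected = 112 × 2 = 224. A subject taking one capsule on each of 112 days scores 112/224 = 50.0%. With one unit per day the score is 112/112 = 100.0%.

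**Step 2: which term depends on the missing kit.** Duration uses dose dates. If the last dose date is missing, SAP 5.4.1 takes the earliest of three dates: return of the last kit, last dispensing plus planned dosing days, and the end-of-treatment or early-termination visit. Only one of these needs a returned kit, and the rule already says to use it only when it is available. The expected count therefore needs no further imputation because of a missing kit. The taken count has no fallback at all.

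**Step 3: effect on the numerator.** Suppose 84 capsules were taken from returned kits, the last kit of 28 is lost, and x of its capsules were swallowed. As written, taken = 84 + 28 = 112 whatever x is. The true count is 84 + x. With the denominator unchanged, the excess is (28 − x)/112, or (28 − x)/224 under the factor of 2.

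| x | True, 1/day | As written, 1/day | Excess | True, 2/day | As written, 2/day | Excess |
|---|---|---|---|---|---|---|
| 0 | 84/112 = 75.0% | 100.0% | 25.0 | 37.5% | 50.0% | 12.5 |
| 14 | 98/112 = 87.5% | 100.0% | 12.5 | 43.75% | 50.0% | 6.25 |
| 28 | 112/112 = 100.0% | 100.0% | 0 | 50.0% | 50.0% | 0 |

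With 7 spares in the lost kit, the as-written count is 119. The excess at one per day then runs from 7/112 = 6.25 to 35/112 = 31.25 points, and half of that (about 3.1 to 15.6) at two per day.

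**Step 4: effect on the categories.** At one per day, the row x = 0 moves from below 80% to the middle band. At two per day no such move occurs for a subject on one capsule daily: 80% of 224 is 179.2, so 180 units are needed. Even with every kit unreturned and 28 spares in all, the score is 140/224 = 62.5%.

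**Step 5: net direction once the denominator is imputed.** Take x = 14 at one per day, so the true value is 87.5%. The reported value is 112/E, where E is the imputed expected count.

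- E = 84 (lost interval dropped from the denominator only): 133.3%.
- E = 112 (no change): 100.0%.
- E = 128: 112/128 = 87.5%, correct by coincidence.
- E = 140: 80.0%, too low.

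The values of E are illustrative. The documents do not say how it would be set.

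**The case against.** The strongest reply is that the rule is unfinished rather than wrong. The details are left to the dataset specification, which might use testimony, and the word for expected may be a slip for taken. Sites may also have entered testimony into the returned counts. None of this can be excluded. But the SAP has already named the quantity to be imputed, and it is the wrong one. If the word is a slip, it still needs correcting in the document that programmers work from.

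A second reply is that the expected count can depend on kit data through SAP 5.4.1. That is true when the last dose date is missing, but that section already handles the case. The fix should point to it.

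Several stronger readings are tempting and should be resisted.

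- *Reported compliance is overstated.* A reader might infer this from Step 3. The documents do not support it as a general statement: the imputed denominator is unspecified, the factor of 2 lowers the whole ratio, and there is no excess if the kit was fully taken and held no spares.
- *Most drop-outs are affected.* No non-return rate is given. Protocol 5.2 asks subjects to return drug at early-termination visits, and Protocol 4.4.1 asks sites to try to complete that visit.
- *Capsule counts are all there is on intake.* Exposure duration is summarised (SAP 11.1), interruptions for adverse events are recorded (Protocol 7.2.2.3) and accountability records are kept (Protocol 5.2).
- *SAP 18 is contradicted.* SAP 18 concerns analyses specified in the protocol, and Protocol section 9 specifies no compliance calculation. The testimony rule sits in the investigational product section. The two documents are not aligned, but an undeclared change of analysis is not shown.

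The testimony rule also covers only drug that can never be returned, which is narrower than any kit not returned.

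**Conclusion.** Wrong as written, in a limited sense. SAP 11.2 imputes the count that dose dates already determine, gives no rule for the count that the missing kit makes unknown, and leaves out Protocol 5.1.6. The numerator can be inflated by 0 to 25 percentage points for one lost 28-capsule kit at one capsule daily over 112 days, or 0 to 12.5 points with the SAP's factor of 2. This rests on an assumed kit size, no spare capsules, an otherwise fully adherent subject and an unchanged denominator. The direction and size of the error in the reported figure cannot be settled from the documents.

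The consequence is modest. Compliance is a descriptive summary for the Safety Analysis Set. It defines no analysis set and enters no efficacy model, so the primary result does not change.

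**What to change.** Reconcile SAP 11.2 with Protocol 5.1.6 by replacing the sentence on unreturned kits with text to this effect:

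*For drug that can never be returned, units taken from the kits concerned are based on subject or caregiver testimony (Protocol 5.1.6). For other unreturned kits, or where no testimony exists, units taken are set to missing for that interval, the interval is left out of both numerator and denominator, and the subject is flagged. The expected count for the remaining intervals stays based on exposure duration, with a missing last dose date handled by SAP 5.4.1.*

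Report the number of subjects with unreturned kits beside the compliance table, and bring the dataset specification into line. The units per day in SAP 11.2 and Protocol 5.1.3 must also be reconciled. That is a separate correction and does not remove this one.

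The cost is a short passage of SAP text and minor programming. Protocol 5.1.6 already calls for the testimony. The downside is a few missing interval values, so that some subjects' compliance will rest on part of their treatment period.
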